5.5.6 Follow-up to Adverse Events

All adverse events occurring during or after the subject has discontinued the study are to be followed up until resolved or judged to be no longer clinically significant, or until they become chronic to the extent that they can be fully characterized.

If during adverse event follow-up, the adverse event progresses to an "SAE", or if a subject experiences a new SAE, the investigator must immediately report the information to the sponsor.

Please refer to [Appendix 2](#) (Liver Safety Monitoring and Assessment) for detailed instructions on liver abnormality follow-up responsibilities related to history of symptoms, concomitant drug use, alcohol use, and recreational drug use.

5.5.7 Monitoring of Common Serious Adverse Events

Common serious adverse events are SAEs commonly anticipated to occur in the study population independent of drug exposure. SAEs classified as “common” are progression to end stage renal disease. This does NOT change your reporting obligations or prevent the need to report an AE meeting the definition of an SAE as detailed above. The purpose of this is to alert you that some events reported as SAEs may not require expedited reporting to the regulatory authorities based on the classification of “common serious adverse events”. The Sponsor will monitor these events throughout the course of the study for any change in frequency. Any changes will be communicated to the participating investigational sites. Investigators must report individual occurrences of these events as stated in Section [5.5.5](#) Reporting of Serious Adverse Events (SAEs).

5.5.8 Procedure in Case of Pregnancy

If a female subject or female partner of a male subject becomes pregnant during the subject’s treatment period or within 12 weeks from the discontinuation of dosing, the investigator should report the information to the delegated CRO as if it is an SAE. Besides completion of the SAE Worksheet, a separate Pregnancy Form should be completed: part A at time of pregnancy reporting and part B when outcome of pregnancy is known. The expected date of delivery or expected date of the end of the pregnancy, last menstruation, estimated fertility date, pregnancy result and neonatal data etc., should be included in this information. Additional details should be provided in part C during the pregnancy and/or after the delivery.

The investigator will follow the medical status of the mother, as well as the fetus, as if the pregnancy is an SAE and will report the outcome to the sponsor.

When the outcome of the pregnancy falls under the criteria for SAEs [spontaneous abortion, induced abortion, stillbirth, death of newborn, congenital anomaly (including anomaly in a miscarried fetus)], the investigator should respond in accordance with the report procedure for SAEs. Additional information regarding the outcome of a pregnancy (which is categorized as an SAE) is mentioned below.

- "Spontaneous abortion" includes abortion and missed abortion.
- Death of an infant within 1 month after birth should be reported as an SAE regardless of its relationship with the study drug.
- If an infant dies more than 1 month after the birth, it should be reported if a relationship between the death and intrauterine exposure to the study drug is judged as "possible" by the investigator.
- In the case of a delivery of a living newborn, the "normality" of the infant is evaluated at the birth.
- "Normality" of the miscarried fetus is evaluated by visual examination unless test results which indicate a congenital anomaly are obtained prior to miscarriage.

5.5.9 Supply of New Information Affecting the Conduct of the Study

When new information becomes available, necessary for conducting the clinical study properly, the sponsor will inform all investigators involved in the clinical study as well as the regulatory authorities, as applicable/needed. Investigators should inform the IRB/IEC of such information when needed.

5.5.10 Emergency Procedures and Management of Overdose

In the event of suspected roxadustat overdose, the subject should receive supportive care and monitoring. If clinically indicated, phlebotomy will be performed [see Section 5.1.5]. The Sponsor's Medical Monitor should be contacted as applicable.

5.6 Test Drug Concentration

For purpose of evaluation of population pharmacokinetics, blood samples will be obtained from all subjects. The intention is to collect 6 blood samples per subject at the following time points:

- A: up to 2 hours prior to dosing
- B: 1 to 2 hours after dosing
- C: 2 to 3 hours after dosing, at least 60 minutes after sample B
- D: 3 to 5 hours after dosing, at least 60 minutes after sample C
- E: 4 to 6 hours after dosing, at least 60 minutes after sample D
- F: 6 to 10 hours after dosing, at least 2 hours after sample E

The blood samples can be collected over 1 to 3 visits, between weeks 2 and 8 of the treatment period:

- samples A, B and C should be collected during the same visit
- samples D and E should be collected on the same visit
- sample F can be collected during the same visit as samples D and E OR during a separate visit. Sample F should be collected as late as possible during the pharmacokinetic visit (last assessment of the visit)
- The investigator is free to choose at which study visits, between weeks 2 and 8 of treatment, to draw the samples and in which order. The study site will inform the subjects on timing and process of the sampling. Based on preference of the study site, there is a choice of 3 sampling schedules to perform the pharmacokinetic samples collection, see Table 8.
- During weeks 1 to 8 subjects will be instructed to record the date and time of study drug intake in the Study Medication Diary (SMD), except for the visit(s) when the study drug is taken in the clinic. The information will be used to record the date and time of roxadustat intake on the day prior to pharmacokinetic sampling and on the day of pharmacokinetic sampling in the eCRF. The date and time of each pharmacokinetic sample and the actual study drug dose taken on the day of sampling will be recorded in the eCRF.

Table 8 Example of Sampling Schedules for Population Pharmacokinetics

Schedule ^a	Pharmacokinetic Visit 1	Pharmacokinetic Visit 2	Pharmacokinetic Visit 3
1	Collect sample A Take study drug in clinic Collect samples B to F	None	None
2 ^a	Collect sample A Take study drug in clinic Collect samples B and C	Take study drug at home Collect samples D to F	None
3 ^a	Collect sample A Take study drug in clinic Collect samples B and C	Take study drug at home Collect sample D and E	Take study drug at home Collect sample F

^a The order of the pharmacokinetic visits for schedule 2 and 3 is a decision for the investigator

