1.2.2.1 Pharmacokinetics and Pharmacodynamics

The pharmacokinetics and pharmacodynamics of roxadustat were characterized in studies in healthy subjects and in dialysis and non-dialysis CKD patients. Roxadustat showed generally dose proportional pharmacokinetics (except at the lowest dose of 0.3 mg/kg); $t_{1/2}$ was 12 to

14 hours in healthy subjects, and 15 to 19 hours in dialysis patients (after single doses of 1 and 2 mg/kg). The exposure was higher in dialysis patients compared to healthy subjects.

With an intermittent dose regimen once per week (QW), twice per week (BIW) or 3 times per week (TIW), no or limited accumulation in mean area under the plasma concentration or C_{max} was observed. Furthermore no evidence was found for time-dependent pharmacokinetics (no auto-induction or inhibition). Roxadustat is highly protein bound and the pharmacokinetics of roxadustat is not affected by dialysis. Metabolites found in urine suggested phase 2 metabolism as the major metabolic pathway. In plasma, parent roxadustat is the main component. The inhibitory potential of roxadustat on cytochrome P450 (CYP) enzymes, based on in vitro studies is limited, and the lowest inhibition constant value was observed for CYP 2C8 (16 μ M). In a clinical drug-drug interaction study with rosiglitazone, a probe drug for CYP 2C8, roxadustat did not show any inhibitory potential on CYP 2C8 in vivo.

Additional drug-drug interaction studies were performed with statins and phosphate binders. Roxadustat increases the AUC_{inf} of simvastatin 1.9-fold, of rosuvastatin 2.9-fold and of atorvastatin 2.0-fold. The AUC_{inf} of roxadustat is decreased 2.9-fold and 1.8-fold respectively by simultaneous administration with the phosphate-binders sevelamer carbonate and calcium acetate. Administration of roxadustat at least 1 hour before or 1 hour after the phosphate binder minimized the interactions.

In healthy adult male subjects (Study [REDACTED]), roxadustat administered orally as a single dose up to 4.0 mg/kg, and QW, BIW, or TIW for 4 weeks at doses up to 3.75 mg/kg, was pharmacodynamically active as evidenced by dose-dependent transient increases in endogenous EPO (starting from single doses of 0.3 mg/kg), increases in reticulocytes (starting from doses of 2 mg/kg), and Hb responses (starting at 3 mg/kg). The mean peak level of plasma EPO following the day 26 dose of 2.0 mg/kg TIW (the high therapeutic dose studied) was 326.3 ± 197.0 mIU/mL.

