5.1 Dosing and Administration of Study Drugs and Other Medications

5.1.1 Dose/Dose Regimen and Administration Period

Following the screening period, eligible subjects will enter the treatment period upon randomization. Subjects will be randomized via IRT to receive roxadustat or placebo. The initial study drug dose is based on the tiered, weight-based dosing scheme [refer to [Table 2](#)]. The first study drug administration should be on the day of randomization, i.e., day 1, after all study assessments have been completed.

Scheduled Visits

During the Treatment period, subjects will attend weekly study visits from day 1 to week 2, followed by every other week study visits from weeks 4 to 24 and thereafter every 4 weeks until the EOT.

Study drug will be dispensed to subjects at each study visit during the treatment period with instructions for self-administration of the tablets on each dosing day, according to the dosing schedule. The study drug tablets are to be swallowed whole with room-temperature drinking water.

All subjects will administer study drug TIW and study drug doses must be administered at least 2 days apart, and no more than 4 days apart. Investigators and subjects should make every effort to keep dosing days and dosing times consistent throughout the study.

Dosing Instructions for Subjects Moving from Protocol v1.0 to Protocol v2.0

Subjects who entered the study under protocol v1.0 should, upon signing the updated informed consent, adapted their dose frequency and dose amount according to the instructions in [Appendix 3](#) Instructions for Subjects Moving from Protocol v1.0 to Protocol v2.0.

There were no adaptations to dose frequency or dose amount for subjects moving from Protocol v2.0 to Protocol v2.1.

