7.2.4 Pharmacokinetic Analysis Set (PKAS)

The PKAS consists of all randomized subjects who meet the following criteria:

- Received at least 1 dose of study drug, and
- At least 1 quantifiable plasma concentration of roxadustat was obtained and dosing and sampling history has been recorded.

Additional details of the population pharmacokinetics (PPK) analysis set will be described in a separate document.

The PKAS will be used for all tables and graphical summaries of the pharmacokinetic data.

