8 OPERATIONAL AND ADMINISTRATIVE CONSIDERATIONS

8.1 Procedure for Clinical Study Quality Control

8.1.1 Data Collection

The investigator or site designee is responsible to ensure that all data in the eCRFs and queries are accurate and complete and that all entries are verifiable with source documents. These documents should be appropriately maintained by the site.

The investigator or site designee will enter data into an eCRF using an Electronic Data Capture (EDC) system.

In the interest of collecting data in the most efficient manner, the investigator or site designee should record data onto the eCRF as soon as possible after the subject visit. The SMD and the questionnaires will be completed by the subject. The investigator or designee should review the diaries and questionnaires for correct completion whilst the subject is at the site. The investigator or site designee will enter only the relevant information from the medication diary (i.e., study medication intake data related to pharmacokinetic sampling) and all questionnaire data directly into the EDC system. (e)CRFs, diaries and questionnaires and any supporting documents should be available for review or retrieval at any given time.

The monitor should verify the data in the eCRFs with source documents and confirm that there are no inconsistencies between them.

Laboratory tests are performed at the central laboratory and specialist laboratory.

Laboratory results will be provided to the investigator who will print and retain the laboratory results and sign abnormalities for their clinical relevance. Laboratory data will be transferred electronically to the Data Management Center at predefined intervals during the study.

The laboratory may provide the Data Manager with a complete and clean copy of the data.

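### Protocol 5.6 sends to the eCRF the intake on the day before PK sampling, but in a compliant subject the dose behind pre-dose sample A was taken two to four days earlier

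*Protocol*

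**What the plan says.** Protocol 5.6 plans six samples per subject over one to three visits in weeks 2 to 8. The first is "A: up to 2 hours prior to dosing"; samples B to F follow a same-day dose, the last at 6 to 10 h. In all three schedules of Table 8 the drug is taken on the sampling day, in the clinic or at home.

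Subjects keep a diary of intake dates and times during weeks 1 to 8, except for intakes in the clinic. On what passes from diary to eCRF, 5.6 says: "The information will be used to record the date and time of roxadustat intake on the day prior to pharmacokinetic sampling". The sampling-day intake is entered too. On the amount, it says that "the actual study drug dose taken on the day of sampling will be recorded in the eCRF".

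Protocol 5.1.1 sets the dosing interval: "study drug doses must be administered at least 2 days apart, and no more than 4 days apart". Protocol 8.1.1 limits data entry: the site "will enter only the relevant information from the medication diary (i.e., study medication intake data related to pharmacokinetic sampling". The same section requires diaries to remain retrievable.

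Protocol 7.6 gives the aim of the analysis as describing roxadustat's pharmacokinetics in the target population and the covariate effects on them. The results go into a separate modelling report.

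**The concern.** A trough concentration can be interpreted only with the time since the dose that produced it. The rule in 5.6 looks for that dose on the day before sampling, and a subject who follows 5.1.1 took no drug that day. The entry is blank whenever dosing is compliant, and is filled only when the minimum interval has been broken.

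The sample concerned is the one that reaches furthest into the elimination phase. If its time after dose does not reach the analysis database, the modeller has to retrieve it from paper, assume an interval or leave the sample out. Thrice-weekly dosing has no single interval to assume: gaps of 48 h and 72 h both occur in an ordinary week, and 96 h is allowed. What is at stake is the estimate of elimination in non-dialysis CKD, and of the covariate effects on it.

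**Working it through.** The documents state no figure on this point, so there is none to reproduce. The check has three steps.

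**1. Which day the previous dose falls on.** Call the sampling day D. It is a dosing day in every Table 8 schedule. With doses 2 to 4 days apart (Protocol 5.1.1), the previous dose falls on D−2, D−3 or D−4. The eCRF rule covers D−1 and D, so the two sets do not overlap for the previous dose.

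**2. Time after dose.** Sample A is drawn 0 to 2 h before the dose on day D. With dosing at a constant clock time:

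- shortest: 2 × 24 − 2 = 46 h
- longest: 4 × 24 = 96 h

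Samples B to F lie at 1 to 10 h after a same-day dose, so A is the only sample beyond 10 h.

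**3. How much the unknown gap matters.** Protocol 1.2.2.1 gives a half-life of 12 to 14 h in healthy subjects and "15 to 19 hours in dialysis patients". It gives none for non-dialysis CKD, so 12 to 19 h is an assumed range. With simple exponential decay, the fraction remaining is 2^(−t / half-life):

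| Half-life | 10 h | 48 h | 72 h | 96 h | Ratio 48 h : 72 h | Ratio 46 h : 96 h |
|---|---|---|---|---|---|---|
| 12 h | 56% | 6.2% | 1.6% | 0.4% | 2^(24/12) = 4.0 | 2^(50/12) = 18 |
| 15 h | 63% | 10.9% | 3.6% | 1.2% | 2^(24/15) = 3.0 | 2^(50/15) = 10 |
| 19 h | 69% | 17.4% | 7.2% | 3.0% | 2^(24/19) = 2.4 | 2^(50/19) = 6.2 |

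At the last post-dose sample, 56 to 69% of the level is still present, so B to F span less than one half-life (10/12 = 0.83; 10/19 = 0.53). Confusing a 48 h gap with a 72 h gap changes the expected level of sample A 2.4- to 4-fold.

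As a worst case, suppose the interval to sample A alone fixed the terminal slope. The apparent half-life would then scale with assumed over true interval: 48/72 = 0.67 (15 h read as 10 h) or 72/48 = 1.5 (15 h read as 22.5 h). A model that fits all six samples jointly across subjects would be moved less.

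**The case against.** **The dose is written down.** A reader might infer that the dose behind sample A is never recorded, or that sample A has no usable time after dose. The documents support neither. The weeks 1 to 8 diary holds the date and time of home intakes, 8.1.1 keeps diaries retrievable, and compliance alone bounds the time at about 46 to 96 h. The gap is in transfer to the eCRF, not in collection. This part of the objection stands.

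**The eCRF page may already ask the right question.** The page is not in the documents, and the description in 8.1.1 is broad enough to cover the previous dosing day. That is possible, but 5.6 is the specific rule and does not say it. A site that follows 5.6 literally would enter nothing. The objection is a reason to check the page, not to leave the text as it is.

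**PK analysis set.** A reader might also infer that subjects fail the condition in Protocol 7.2.4: "At least 1 quantifiable plasma concentration of roxadustat was obtained and dosing and sampling history has been recorded". That condition is applied per subject, and samples B to F, with their recorded same-day dose, can meet it. Nothing in the documents shows that anyone would be excluded on this ground.

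**Information in sample A.** On the figures above, the level may be only 0.4 to 17% of what the previous dose produced. No quantification limit is given, so how much sample A contributes to the elimination estimate is unknown. This stands, and it limits the claim to a risk of bias or lost precision.

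**Amount.** SAP 6.5.4 says that the prescribed dose at each visit is already captured in the eCRF, so much of the amount information exists. It needs linking, because dose reviews start at week 4 (Protocol 5.1.2), inside the sampling window, and the preceding dose can differ from that of the sampling day.

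**Conclusion.** The point holds as a mismatch between two current rules. Under 5.1.1 the entry specified in 5.6 cannot contain the dose behind sample A in a compliant subject, so its date and time remain in the diary. Sections 5.6 and 5.1.1 need to be reconciled on what is captured.

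The size is a 2.4- to 4-fold difference in expected level between the usual 48 h and 72 h gaps, and 6- to 18-fold across the whole permitted range. These figures rest on simple exponential decay, a half-life range borrowed from healthy subjects and dialysis patients, and dosing at a constant clock time. The half-life factors of 0.67 and 1.5 are worst cases only.

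The consequence is confined to the population PK analysis, which has its own plan and report. No efficacy or safety endpoint depends on it. It deserves correction because the needed record already exists and the loss is avoidable.

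**What to change.** Reword Protocol 5.6 so that the eCRF takes from the diary the date and time of the last roxadustat intake before the PK sampling day, whatever the calendar day, as well as the intake on the sampling day. The amount of that previous dose should be recorded with it or linked from the dosing eCRF. Check the eCRF PK page against this wording and amend it if it asks only about the preceding day. For subjects already sampled, transcribe the entry from the retained diaries before database lock.

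The cost is a small amount of data entry and, if needed, a change to the eCRF page. It needs no new samples or visits and no change to dosing.

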5.6.1 Blood Sample for Roxadustat Pharmacokinetic Analysis

Samples of venous blood (3 mL) for bioanalysis of roxadustat will be collected into appropriately labeled tubes containing sodium-heparin as anticoagulant. Immediately after collection, blood samples will be kept on melting ice until ready for centrifugation, which must be done within 30 minutes of collection. Blood samples will be centrifuged at 1500 g for 10 minutes at room temperature in order to obtain plasma. Plasma will be harvested and transferred into an appropriately labeled 3.6 mL polypropylene storage tube and stored at -20°C or below, within 30 minutes of centrifugation.

Samples will be stored frozen at the site until shipment.

Samples will be sent to the central laboratory packed with sufficient dry ice to keep the samples frozen. Further details will be provided in the laboratory manual.

5.7 Other Measurements, Assessments, or Methods

Serum levels of albumin and α 1-AGP will be included as covariate in the pharmacokinetic analysis, since both albumin and α 1-AGP is involved in plasma protein binding of roxadustat.

Serum albumin and α 1-AGP will be analyzed by the central laboratory using a standardized assay. To perform the analysis, 2 mL blood samples will be collected on the same day as pharmacokinetic sampling is performed (1-3 visits). If 1 or more pharmacokinetic samples are taken at a visit, 1 α 1-AGP sample should be taken at that visit as well.

After blood sampling, serum separator tube (SST), samples should be kept in an upright position for at least 30 minutes at room temperature to allow blood clotting. The tubes should not be refrigerated or opened during this time. After this clotting period, the SST will be centrifuged for 10 minutes at 1500 g at room temperature within the next 30 minutes (i.e., within 1 hour of sampling). Serum from each tube will be harvested and transferred into a properly labeled polypropylene tube and stored at -20°C or below until shipment to the central laboratory where they will be analyzed.

5.7.1 Heparin in Serum

For the determination of heparin, serum samples will be drawn at the visits as indicated in [Table 1](#). All details on the processing of the samples, storage and shipment conditions will be provided in the laboratory manual. Results will be blinded to site personnel and the Sponsor.

5.7.2 Archival of Serum Samples for Biomarker Analysis

Serum samples will be drawn at the visits as indicated in [Table 1](#). The processed samples will be stored and archived for potential future analysis of relevant biomarkers, linked with the efficacy or safety of the study drugs, prognosis and outcomes. These archival samples will be destroyed (if not used in total), maximally 5 years after the last subject completed the study. All details on the processing of the samples, storage and shipment conditions will be provided in the laboratory manual.

5.7.3 Archival of Urine Samples for Biomarker Analysis

Urine samples will be drawn at the timepoints as indicated in [Table 1](#). The processed samples will be stored and archived for potential future analysis of relevant biomarkers. All details on the processing of the samples, storage and shipment conditions will be provided in the laboratory manual.

